1.1. Hypotheses

High peak levels of tacrolimus predispose renal transplant recipients to BK infection. Conversion of tacrolimus to Envarsus will reduce incidence of BK viruria, viremia, and nephropathy.

1.2. Primary Safety Objective

Envarsus has shown a lower side effect profile in the ASTCOFF study but still carries the same potential risks as tacrolimus. Incidence of BK infection, graft loss, and other adverse events will be tracked.

1.3. Primary Efficacy Objective

The primary efficacy endpoint of the study is the composite of BK Virus infection, including viruria > 500 copies, viremia > 500 copies, or nephropathy as defined by Banff classification (sv 40 positivity with or without tubulitis or if/ta).

1.4. Secondary Efficacy Objective

The secondary end-points will assess incidence of rejection, graft failure, graft dysfunction as defined by >15% decrease in estimated glomerular filtration rate (eGFR), and proteinuria.

2. Background and Rationale

2.1. Background and Scientific Rationale

2.1.1. BK Viral Infection

Development of BK Infection post transplant is largely attributed to reactivation of virus in the donor allograft. Risk factors are multifactorial and can not be linked to an individual immunosuppression agent. Degree of immunosuppression is the most consistent risk factor, and reduction of immunosuppression is the most effective treatment. Rates of BK viruria, viremia, and nephropathy are 40%, 20%, and 1-10% respectively^{10,19}. BK virus nephropathy (BKVN) is strongly and independently associated with poor graft survival. BKVN has a high graft failure rate at over 50%. Peak incidence of BK infection is in the first year post transplant.

2.1.2. Etiology of BK Infection

Several different studies identify donor and recipient characteristics as risk factors for BK infection. Several studies conflict on the role of depletional induction with thymoglobulin or campath versus non depletional induction with simulect as risk factors. Several studies conflict regarding the number of immunosuppression agents (two vs. three, generally steroid free vs. not) as risk factors. Studies show conflicting risks regarding tacrolimus vs cyclosporine regimens vs. CNI free regimens. Injury to the uroepithelial pathway has also been reported as a risk factor. There has not been one consistent identifiable cause of BK infection post transplant.

2.2. Rationale for use of Envarsus

Rapid metabolizers have an allelic variation at cyp 450 3a5 and require higher doses of tacrolimus to achieve goal trough drug levels for prevention of rejection. These patients have higher incidence of side effects related to high peak levels and have periods of heightened drug exposure. The use of a concentration/drug dose ratio < 1 for tacrolimus has been validated as an identifier for rapid metabolizers.¹⁻⁴ The use of Envarsus in place of short acting tacrolimus has been shown to provide equitable drug exposure and efficacy with respect to prevention of rejection and decreased side effects due to lower peak levels. It has also been shown to achieve therapeutic trough levels with lower dosing.⁵⁻⁹

2.3. Clinical Studies of Concentration/Dose (C/D) Ratios and BK infection 2.3.1. Validation of C/D Ratio

In the paper by Tholking³ et al, renal transplant patients were grouped as slow or fast metabolizers according to their C/D ratio. Fast metabolizers had higher incidence of graft dysfunction, calcineurin inhibitor toxicity, and BK virus nephropathy. The use of C/D ratio as a marker of cyp 450 3a5 metabolism was further validated in several studies^{1,2,4}.

2.3.2. Clinical Studies of Rapid Metabolizers and BK Infection

Tholking et al have demonstrated and increased association with BK infection among transplant patients with low C/D ratios compared to those with high C/D ratios.

In a single center retrospective study¹ of 248 patients designed to investigate effect of metabolism on renal function, patients were grouped according to their C/D ratio (< 1 for fast metabolizers, and >1.55 for slow metabolizers) and had eGFR assessed at 2, 3, 6, 12, and 24 months. Incidence of BK viremia was 8% in the fast group and 1% in the slow group. BKVN was only diagnosed in the fast group with a 4% incidence.

The fast metabolizer group also had significantly higher rates of CNI nephrotoxicity. The authors hypothesized that these findings are related to overexposure of tacrolimus during the peak hours after tacrolimus intake.

A second retrospective study⁴ assessed C/D ratio in 192 renal transplant patients, 92 of whom had BK viremia and 92 whom did not. Patients with BK viremia had lower tacrolimus C/D ratios at 1, 3, and 6 months post transplant.

2.4 Clinical Studies of Envarsus

2.4.1

Data from a randomized, double blinded study of Envarsus versus tacrolimus by Budde⁵ and data from the open label phase III MELT Trial both demonstrated non inferiority of Envarsus.

In the phase III RCT by Budde, de novo kidney transplant patients were placed on

tacrolimus vs Envarsus along with mycophenolate mofetil (MMF) and prednisone and followed for endpoints of death, graft failure, or biopsy proven rejection. At 12 months, overall survival was 97% in both Envarsus and tacrolimus recipients; graft survival was 97 and 96%, respectively, and graft and patient survival combined was 94 % in both groups. The incidence of clinically suspected and treated rejection was 14 versus 16% in Envarsus versus tacrolimus recipients, and no significant treatment differences were found in the number of biopsy-proven acute rejection episodes. A total of 195 Envarsus and 199 tacrolimus recipients completed 24 months of follow-up on their assigned treatment. At 24 months, the treatment failure rate was 23.1 versus 27.3 %, respectively, with a treatment difference of 4.14 (95 % CI 11.38 to +3.17), again demonstrating noninferiority. The incidence of the individual events comprising treatment failure were similar between treatment groups at 24 months: biopsy-proven acute rejection occurred in 17.2 % of Envarsus and 18.2 % of tacrolimus recipients, graft failure in 4.1 and 5.5 %, respectively, death in 4.1 and 4.7 %, and lost to follow-up in 1.5 and 2.9 %. Renal function was also similar between treatment groups over the 24month period. The total daily tacrolimus dose was 25 % lower in Envarsus than in tacrolimus recipients in the second year of treatment; Ctrough values remained similar.

2.4.2

In the conversion study or MELT Trial⁶, findings at 12 months were similar with respect to non inferiority for endpoints of death, graft failure or rejection. The primary endpoint was the efficacy failure rate at 12 months (*n*= 162 in each group); efficacy failure comprised death, graft loss, loss to follow-up or locally read biopsy-proven acute rejection. Envarsus was noninferior to tacrolimus with regard to the efficacy failure rate at 12 months in stable, previously treated kidney transplant recipients. The biopsy-proven acute rejection rate was 0.6 versus 2.5 %, respectively. At 12 months, patient survival was 98.8 % in the Envarsus and 99.4 % in the tacrolimus group. The death-censored graft survival rate at 12 months was 100 % in both groups.

Envarsus has an oral bioavailability that is 40% higher than that of tacrolimus in kidney transplant recipients. Moreover, Envarsus is associated with a significantly reduced peak-trough fluctuation ratio and a significantly longer time to C_{max} than tacrolimus, as well as significantly lower mean values for percentage degree of fluctuation and percentage degree of swing. Envarsus was also associated with a significantly lower C_{max} .

2.4.3 Post Hoc Analyses

Exploratory, post-hoc, subgroup analyses of pooled data from both phase III trials found that Envarsus was associated with a significantly lower treatment failure rate than tacrolimus in Black patients and patients older than 65. Patient numbers were much lower for Black (93) than non-Black (768) patients and for patients aged >65 (84) than those aged <65 (777) years.

2.4.4 Pharmacokinetic Study

The ASTCOFF⁷ is a cross over PK study that randomized stable kidney transplant patients in a 1:1:0.8 dose conversion for Tacrolimus-IR, Tacrolimus-ER, and Envarsus. Significantly higher exposure on a per mg basis, lower intraday fluctuation and longer time to C_{max} were associated with Envarsus.

3. Study Design

3.1. Description of Study Design

This will be a single center prospective case control study. We expect 40% of patients will develop BK viruria, 20% BK viremia, 5% BK viral nephropathy (BKVN). Patients will be managed using standard of care for our center (thymoglobulin induction, tacrolimus/mycophenolate/prednisone). Target tacrolimus level is 8-12 ng/mL for the first 6 months post transplant and 6-9 ng/mL thereafter. BK urine/serum is routinely monitored during the first year post transplant. A population of 100 patients is calculated to show significant difference for p value < 0.05.

Population:

Study Group: Post transplant patients (kidney transplant alone) with standard of care immunosuppression, no prior rejection, prior BK or opportunistic infection, and negative BK screening at post-transplant month 1, who have a tacrolimus concentration/dose of < 1 and a steady state therapeutic level will be eligible. Patients who consent to participate will be converted to Envarsus at 20% reduction in tacrolimus dose.

Control Group: Post transplant patients (kidney transplant alone performed between 10-2016 and time of consideration for study control group) with standard of care immunosuppression, no prior rejection, prior BK or opportunistic infection, who had a negative BK screening at post-transplant month 1 and tacrolimus concentration/dose of < 1 at post-transplant month 1, and BK data available for months 2, 3, 6, 9, 12 post transplant.

Study visits: Post-transplant Months 2, 3, 6, 9, 12

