4.1. Enrollment Eligibility Criteria

4.1.1. Inclusion Criteria

Individuals who meet all of the following criteria are eligible for enrollment as study participants:

- 1. Patient must be able to understand and provide informed consent
- 2. Age \geq 18 years of age at the time of study entry
- 3. Recipient of a deceased or living donor kidney transplantation
- Maintenance immunosuppression consisting of tacrolimus/MMF/MPA (≥1000 mg/720 mg daily) ± prednisone (≤10 mg/day)
- 5. Patient is less than or at 8 weeks post transplant with a negative serum BK Virus screen at 3-4 weeks post transplant
- 6. Patient has a tacrolimus drug dose/concentration of > 1 with therapeutic tacrolimus levels.
- 7. Women of childbearing potential defined as all women physiologically capable of becoming pregnant, must have reviewed Mycophenolate REMS and have a negative pregnancy test upon study entry.
- 8. Female (and male) subjects with reproductive potential must agree to use a highly effective method of birth control for the duration of the study. Please note that according to the US product information for MMF/MPA, two reliable forms of contraception must be used simultaneously unless female sterilization, male sterilization, post-menopausal status or total abstinence is the chosen method.

Acceptable methods of highly effective birth control include:

- Condom with spermicide
- Diaphragm and sperm ide
- Cervical cap and spermicide
- Use of oral, injected or implanted hormonal methods of contraception or other forms of hormonal contraception that have comparable efficacy (failure rate <1%), for example hormone vaginal ring or transdermal hormone contraction
- Intrauterine device (IUD)

Female sterilization (have had surgical bilateral oophorectomy with or without hysterectomy) or tubal ligation at least six weeks prior to screening.

Male sterilization at least 6 months prior to screening. For female subjects on the study, the vasectomized male partner should be the sole partner for that subject.

Post menopausal women defined as being not of child bearing potential if they have had 12 months of natural (spontaneous) amenorrhea.

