11.7. Reporting of Other Safety Information

An investigator shall notify the site IRB according to the site's IRB guidelines when an "unanticipated problem involving risks to participants or others" is identified, which is not otherwise reportable as an adverse event.

12. Statistical Considerations and Analytical Plan

This is a single center prospective study comparing incidence of BK infection in rapid metabolizers converted from tacrolimus to Envarsus against a recent historical control of rapidly metabolizing recipients who had BK screening at similar points, but remained on tacrolimus.

This study has both safety and efficacy endpoints.

We will use standard descriptive statistics for continuous and categorical data to define adverse events, and clinical outcomes as noted above. Analysis will be undertaken utilizing UAB statistical support in the School of Public Health and Transplant Quality, Informatics and Outcomes.

The enrollment plan is based on a power calculation. A population of 100 patients is calculated

to show significant difference for p value < 0.05.

Our results will be submitted to national/international nephrology/transplant meetings, and as a primary manuscript reporting the primary efficacy and safety data, and secondary manuscripts reporting different secondary endpoints, as appropriate.

We expect the changes over time in these assays to be approximately linear. If after examination of the data, this appears to not be the case, then we will either transform the assay measures or model the time axis time points as an unordered factor (similar to repeated measures ANOVA, but without the requirement for fully balanced data).

We will use descriptive analyses to summarize subject characteristics of our study population. Dichotomous variables will be summarized as proportions with 95% confidence intervals. Continuous variables will be summarized using means, standard deviations, and 95% confidence intervals if they are symmetric and unimodal. Otherwise, they will be summarized using the median and the interquartile range. Simple t-, chi-squared, or Fisher's exact test, as appropriate, will be used to compare quantitative measures across treatment groups. The following variables will be summarized:

- Baseline and demographic characteristics
- Use of concomitant medications
- Reasons for early termination
- All reportable AEs

No formal interim analyses of this study are planned.

13. Identification and Access to Source Data

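### Study patients must have a steady-state therapeutic tacrolimus level as well as C/D below 1, while historical controls need only the ratio at month 1

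*Combined protocol and SAP*

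**What the plan says.** Section 3.1 sets out the two groups under Population. A study patient must be among those "who have a tacrolimus concentration/dose of < 1 and a steady state therapeutic level will be eligible". Inclusion criterion 6 in Section 4.1.1 states the same ratio inverted and keeps the level condition: "Patient has a tacrolimus drug dose/concentration of > 1 with therapeutic tacrolimus levels". A control must have "tacrolimus concentration/dose of < 1 at post-transplant month 1, and BK data available for months 2, 3, 6, 9, 12 post transplant". Nothing is said about whether the control's level was in range or settled.

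Section 12 describes the comparator only as a "recent historical control of rapidly metabolizing recipients who had BK screening at similar points, but remained on tacrolimus". It names t, chi-squared and Fisher tests for comparing the groups. It also mentions modelling of unspecified assays over time, but no adjustment for tacrolimus level, dose or C/D.

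On the marker itself, Section 2.2 says: "The use of a concentration/drug dose ratio < 1 for tacrolimus has been validated as an identifier for rapid metabolizers". On management, Section 3.1 says: "Target tacrolimus level is 8-12 ng/mL for the first 6 months post transplant and 6-9 ng/mL thereafter". Section 6.1.1 repeats these targets as the centre's standard of care.

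**The concern.** The hypothesis in Section 1.1 is that high tacrolimus peaks predispose to BK infection. The C/D ratio, with the level and dose behind it, is how the plan picks out patients exposed to such peaks. The control group is historical and not randomised, so selecting both groups by the same rule on this variable is one of the few protections the comparison has.

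The written rules differ. The study group is restricted to patients whose level has settled in the therapeutic range, and the control group is not. If controls outside that restriction have a different BK risk, the groups differ before anyone is converted, and an unadjusted comparison cannot separate that difference from the effect of Envarsus.

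**Working it through.** The plan gives no figure on this point to reproduce. Its one design figure, 100 patients, comes without a treated-group rate, power or allocation, and nothing below depends on it.

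**1. The criteria side by side**

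| Condition | Study group | Controls |
|---|---|---|
| C/D cut-off | below 1 (3.1; 4.1.1 item 6) | below 1 (3.1) |
| Steady state | required (3.1) | not stated |
| Therapeutic level | required (3.1; 4.1.1 item 6) | not stated |
| Time of qualifying ratio | not stated; eligibility screen at about month 1 (9.4, Appendix 1) | month 1 (3.1) |

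Criterion 6 is consistent with Section 3.1: for positive C and D, D/C > 1 is the same condition as C/D < 1.

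**2. Does any other text extend the level condition to controls?** Section 4.1.1 cannot be read across. It requires consent, and its item 5 reads "Patient is less than or at 8 weeks post transplant with a negative serum BK Virus screen at 3-4 weeks post transplant", whereas a control must already have BK data to month 12. Section 12 adds no level condition. The 8-12 ng/mL range in Sections 3.1 and 6.1.1 is a treatment target, not a selection rule for controls.

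**3. Who qualifies under each rule.** Assumptions, because the units are not stated: C in ng/mL, D in total mg/day, therapeutic meaning 8-12 ng/mL at entry.

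- C/D < 1 means D > C. With C of at least 8, every study patient has D > 8 mg/day; at C = 12, D > 12 mg/day.
- 5 ng/mL on 6 mg/day: 5/6 = 0.83. Below 1, level under range. Qualifies as a control only.
- 15 ng/mL on 16 mg/day: 15/16 = 0.94. Below 1, level over range. Qualifies as a control only.

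The control rule therefore lets in values both below and above what the study rule allows. An in-range level that has not settled would also pass for a control only.

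**4. What this could do to the control rate.** Let s be the share of controls who would fail the study-group condition, q their BK rate, and p the rate in the other controls. The observed control rate is (1 - s)p + sq, so the shift is s(q - p).

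Take p = 0.40, the viruria rate expected in Section 3.1, as a stand-in for the composite. The documents give neither s nor q. For illustration, assume s of 0.10 to 0.30:

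- q = 0.20: shift = 0.10 × (-0.20) to 0.30 × (-0.20) = -0.02 to -0.06; control rate 38% to 34%.
- q = 0.60: shift = 0.10 × 0.20 to 0.30 × 0.20 = +0.02 to +0.06; control rate 42% to 46%.
- q = 0.40: no shift, whatever s is.

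The sign depends entirely on q - p. Section 2.1.1 calls the degree of immunosuppression the most consistent risk factor, which makes a lower q plausible for sub-target controls and a higher q plausible for supratherapeutic ones. Both kinds may be in the pool and partly cancel.

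**The case against.** Controls were on the centre's standard of care, which aims at 8-12 ng/mL in the first six months, so many probably had in-range levels at month 1 and the practical gap may be narrow. That is fair, and it limits the likely size. But being treated to a target is not the same as having reached it. The plan makes attainment an entry condition for study patients, and Section 2.2 says rapid metabolizers need higher doses to get to goal.

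A second objection is that C/D < 1 alone is the marker that Section 2.2 calls validated. This stands against one tempting inference: that controls with off-target levels are misclassified, or that the groups use different definitions of a rapid metabolizer. By the plan's own definition, a control at 5 ng/mL on 6 mg/day is a rapid metabolizer. The fault is that an additional condition applies to one group only.

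A reader might also infer from the 8-week limit that study patients can qualify at any time up to week 8. The documents do not establish that. Section 9.4 puts the eligibility screen at about one month. Appendix 1 marks eligibility only in the screening column, at or before 4 weeks, with a tacrolimus level drawn then; 8 weeks is the enrolment limit. Because a level is also drawn at enrolment and no month is attached to the study group's ratio, the timing is ambiguous, not shown to differ.

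**Conclusion.** The asymmetry is in the text and nothing elsewhere removes it: one group is selected on C/D plus a settled therapeutic level, the other on C/D alone, and the planned tests do not correct for this.

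Its effect is of unknown size and unknown direction. The share of controls affected and their BK risk are not given. The shifts of 2 to 6 points either way rest on assumed inputs and show scale only. It would go too far to conclude that the rule creates an apparent benefit for Envarsus: a lower-risk group of sub-target controls would hide a benefit, and only a higher-risk group would inflate one. The worked examples also rest on the assumed units and on reading therapeutic as 8-12 ng/mL.

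This is an avoidable source of selection bias within an already non-randomised comparison. It is worth removing because removal is cheap, not because harm has been shown.

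**What to change.** - In Section 3.1, add to the control definition the condition already used for the study group: a steady-state level within the centre's target range at the qualifying month-1 measurement. Write down one working definition of steady state and use it for both groups.
- State that the study group's qualifying C/D is the one at the screening visit at about month 1 (Section 9.4, Appendix 1).
- If this leaves too few controls, keep the wider pool, report month-1 level and dose in both groups, and prespecify a sensitivity analysis restricted to controls who meet the study-group criterion.

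Cost: computing a control's month-1 ratio already needs one level and one dose, so the range condition is a filter on those values. Confirming steady state needs some chart review of dose history, which the documents do not say is collected for controls. The control pool will shrink by an amount that the documents do not allow to be estimated.

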3.3. Primary Efficacy Endpoint

The efficacy primary endpoint of the study is the composite of BK Virus Infection, including viruria > 500 copies, viremia > 500 copies, or nephropathy as defined by Banff classification (g/msv 40 positivity with or without tubulitis or if/ta).

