4.1.2 Exclusion Criteria

Individuals who meet any of these criteria are not eligible for enrollment as study participants:

- 1. Inability or unwillingness of a patient to give written informed consent or comply with study protocol
- 2. History of graft loss from acute rejection within 1 year after any previous kidney transplant
- 3. History of previous liver, heart, pancreas, or lung transplant
- 4. History of cellular rejection of current allograft prior to enrollment
- 5. Serum BK virus ≥500 copies/mL by PCR at the time of study entry
- 6. Female subjects who are pregnant or breast feeding
- 7. Participation in any other studies with investigational drugs or regimens in the preceding year from the time of study entry
- 8. Any condition or prior treatment which, in the opinion of the investigator, precludes study participation
- 9. Patients requiring the use of azathioprine or mTOR inhibitors
- 10. Patients with active peptic ulcer disease

5. Investigational Agent: Envarsus

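### Control selection has no calendar closing date, no take-all rule and no blinding to BK results, so nothing prevents controls being chosen with outcomes known

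*Combined protocol and SAP*

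**What the plan says.** Section 3.1 (Control Group) sets the period for control transplants as "kidney transplant alone performed between 10-2016 and time of consideration for study control group". The opening month is fixed. The end is an event with no date, and it is not tied to first enrolment. Controls must be negative on the month-1 BK screen, have a concentration/dose ratio below 1 at month 1, and have "BK data available for months 2, 3, 6, 9, 12 post transplant".

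The same section lists "Study visits: Post-transplant Months 2, 3, 6, 9, 12", and section 3.3 makes the primary endpoint a composite of "viruria > 500 copies, viremia > 500 copies, or nephropathy as defined by Banff classification".

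The study group is formed by consent: "Patients who consent to participate will be converted to Envarsus at 20% reduction in tacrolimus dose".

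Section 12 describes the comparison as one "against a recent historical control of rapidly metabolizing recipients" who remained on tacrolimus. It plans simple unadjusted tests. Neither section gives a number of controls, a rule that all or consecutive eligible patients enter, a matching rule, or who selects and what they may see.

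**The concern.** There is no randomisation, so the control BK rate is half of the primary comparison. Two features of the text leave that rate exposed.

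First, eligibility is settled from the part of the chart that holds the outcome. With no take-all rule, no stated number and no fixed end date, both the choice of charts and the point at which searching stops remain open after outcomes are known. Adjusting for baseline covariates cannot undo selection on the outcome, and the plan specifies no adjustment in any case.

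Second, the open-ended window may admit patients transplanted while the trial was enrolling. At a single centre these are contemporaries who did not enter the study group. Some may have refused, some may not have been approached, and some may have been kept out under a criterion such as "Any condition or prior treatment which, in the opinion of the investigator, precludes study participation" (section 4.1.2). Such patients may differ in BK risk from those who were converted.

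**Working it through.** **No plan figure to reproduce.** The only design figure is 100 patients at p < 0.05. Power, effect size, sidedness, allocation and number of controls are not stated, so it can be neither reproduced nor refuted. This point does not dispute it.

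**Step 1: eligibility against outcome.** Control eligibility needs BK data at months 2, 3, 6, 9 and 12. The study visits are months 2, 3, 6, 9 and 12. The viruria and viremia parts of the endpoint come from those same tests. Eligibility and outcome therefore share one set of records.

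**Step 2: when a contemporary can become a control.** A control must have a month-12 BK result, so the transplant lies about 12 months before the control is confirmed. A patient transplanted after opening can therefore be confirmed only more than about 12 months after opening. Section 3.1 permits this; the word historical in section 12 suggests it is not intended. Neither section gives a date that settles it.

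**Step 3: scale (illustration only).** Assumptions: no drug effect; a true composite rate p = 0.40 in both groups; equal groups; two-sided 0.05 chi-squared test without continuity correction. The 40% is the viruria expectation in section 3.1. The plan gives no composite rate; from its components (40%, 20%, 5%) it would lie between 40% if fully nested and 65% if none overlap.

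Let w be the chance that a BK-positive chart is chosen relative to a BK-negative one, with a large chart pool:

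control rate = p·w / (p·w + 1 − p)

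- w = 1.25 (20% of BK-negative charts left out): 0.50/1.10 = 45.5%
- w = 1.5: 0.60/1.20 = 50%
- w = 2 (half of BK-negative charts left out): 0.80/1.40 = 57.1%
- w = 0.75: 0.30/0.90 = 33.3%

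Separately, if 20% of controls were non-enrolled contemporaries with a 60% rate: 0.8 × 0.40 + 0.2 × 0.60 = 44%.

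The chance of a false significant result favouring Envarsus is the sum of the binomial probabilities of all pairs (a control events, b Envarsus events) with (a − b)/n ÷ √(2q(1 − q)/n) > 1.96, where q = (a + b)/(2n):

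| Scenario | Control rate | 50 per group | 100 per group |
|---|---|---|---|
| No selection | 40% | 2.6% | 2.6% |
| 20% contemporaries at 60% | 44% | 6.4% | 9% |
| w = 1.25 | 45.5% | 8.5% | 12% |
| w = 1.5 | 50% | 18% | 31% |
| w = 2 | 57.1% | 43% | 70% |
| w = 0.75 | 33.3% | 0.4% | 0.2% |

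In the last row the error runs the other way: the chance of a false significant result against Envarsus is about 10% with 50 per group. The values of w, the 20% share and the 60% rate are assumptions, and the documents do not bound them.

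**The case against.** Several stronger readings are tempting, and the documents do not support them.

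- *Staff have to read later BK values to confirm a control.* The text requires data to be available. A check of test dates would meet it without any value being seen. The plan provides no such step, however, so the exposure remains possible though not required.
- *Every control transplanted after opening declined or was passed over.* Such a patient might also have failed a criterion set for the study group only. Section 3.1 admits to that group those "who have a tacrolimus concentration/dose of < 1 and a steady state therapeutic level will be eligible", and the therapeutic-level part is not stated for controls. Other such criteria are the 8-week limit (section 4.1.1) and, in section 4.1.2, serum BK at entry, another study in the preceding year, or active peptic ulcer disease. The patient might also have been transplanted after enrolment filled.
- *The window certainly stays open during enrolment.* The time of consideration may be a single date on which the whole group is assembled. If that falls within about a year of opening, the month-12 requirement means that every control was transplanted before opening, and the second concern disappears.
- *Controls are being picked on outcome.* Section 3.1 defines the group by criteria and describes no sampling or quota. Silence about consecutive inclusion is under-specification and shows no intent.

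It is also fair to say that routine BK monitoring in the first year may mean the availability rule excludes few patients. A hard cut-off at first enrolment would also remove any concurrent controls, which could help in judging drift over calendar time.

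What remains is that no date, take-all rule or blinding is stated, and that sections 3.1 and 12 do not settle whether contemporaries may enter.

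**Conclusion.** The point holds as a gap in the selection rule. The control window lacks a calendar end, eligibility uses records from the outcome period, and nothing prevents outcome-aware choice or stopping in an unadjusted, non-randomised comparison. Whether non-enrolled contemporaries enter depends on when controls are assembled, which the documents do not say; sections 3.1 and 12 must be reconciled on this.

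The size and direction of any bias are unknown. The table shows only that modest preferences would matter if they occurred: under its assumptions, the 2.6% chance of a false benefit rises to between 6.4% and 43% at 50 per group, and the opposite preference would mask a real benefit. The change is worth making because it is cheap and removes a doubt that no later analysis can resolve.

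**What to change.** In sections 3.1 and 12:

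1. State a fixed calendar window for control transplants, with both dates, and use the same description of the control group in both sections.
2. Take every consecutive recipient in that window who meets the month-1 criteria.
3. Build the list from an extract holding only data up to the month-1 screen, and freeze it before later BK results are linked.
4. Replace the requirement for BK data at all five months with one rule for missing BK tests, applied equally to both groups. This is needed once the list is frozen on month-1 data. It also stops controls being dropped for early death, graft loss or loss to follow-up when no matching rule exists for the study group.
5. Flag any control transplanted after the first study enrolment, and repeat the primary comparison without them. This keeps concurrent controls in the main analysis while showing whether they drive the result.

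The cost is protocol wording and a two-step data pull. Some controls will have incomplete BK tests, and the sensitivity analysis may have fewer recent controls. How many cannot be said, because the documents give neither a control count nor enrolment dates. No patient's care changes.
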